More detail is needed regarding the analysis of cost effectiveness data. We have described exactly how the cost effectiveness data for this secondary objective will be analyzed. We will complete descriptive analyses to estimate and report the incremental costs associated with the CGS and CGS+BT interventions relative to SC and, if there are group differences in the frequencies of emergency room visits or hospitalizations, we will calculate the incremental cost for each such event prevented by the CGS and CGS+BT regimens.

SUMMARY

We believe that we have carefully and thoroughly addressed each concern expressed in the prior critique and that we have submitted a substantially stronger application as a result. We hope that the reviewers concur with this assessment. Substantive changes appear in italics throughout the research plan.

2. SPECIFIC AIMS This revised application responds to NIH Announcement #PA-07-097 "Chronic Illness Self-Management in Children and Adolescents". It addresses the priorities stated in that announcement related to testing interventions targeting improved self-management of pediatric chronic diseases.

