for research purposes only (recruiting, informed consent, questionnaire administration, data transmission) will be excluded. Clinicians will record the duration, nature and purpose of each clinical contact (clinic, phone, e-mail) or other clinical activity (downloading, CGS or meter maintenance, provision of supplies) with each patient using methods employed successfully in [name] intensive therapy trial. The ratio of time dedicated to Intensive Therapy patients to that for Standard Care patients during that study was about 4.5:1 for Diabetes Nurses, 3:1 for Dietitians and Psychologists and 1.3:1 for Physicians. The similarity of these estimates to those reported in the DCCT supports this method as a valid estimate of the degree of health professional time devoted to patients receiving varied interventions, permitting a reasonable derivation of the per-patient incremental costs for the CGS and CGS+BT regimens relative to the SC regimen. *We anticipate that the personnel time for the CGS groups will decline as the study proceeds, but distributing the observation periods throughout the study will yield a valid estimate of the relative personnel requirements for each condition. From these "time-sampled" cost estimates we will extrapolate the per-patient personnel costs of each of three conditions for the entire 9-month Randomized Phase. At quarterly clinic visits, parents will report the occurrence of hospitalizations, emergency room visits, and clinic visits. These reports will be verified by the Diabetes Nurse by medical records checks whenever possible. The costs for hospitalizations, ER visits and clinic visits will be obtained from the involved medical facilities. The retail costs of CGS devices and supplies will be included. Cost effectiveness of the CGS and CGS+BT will be evaluated descriptively both by direct comparison of the estimated costs of SC, CGS and CGS+BT and by reporting the cost per 0.5% improvement in HbA_{1c} during the study for each group. These descriptive analyses will also focus on whether the added costs associated with the CGS regimens are offset by reductions in health care utilization (clinic visits, emergency room visits, hospitalizations) for those groups relative to Standard Care.*

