- Incorporation of therapy advances that emerge before or during the study. The SC group may not use a CGS device during the 9-month randomization phase except in the blinded 7-day CGS use periods.
- *A "rescue procedure" will be employed for any youth whose HbA_{1c} remains above 9% for 2 consecutive visits or whose HbA_{1c} increases by more than 1.0% over baseline or who has more than one episode of severe hypoglycemia. As would typify clinical practices with similar patients, this will consist of offering monthly clinic visits with a diabetes nurse, weekly telephone consultation with the nurse and referral to a dietitian, social worker, psychologist or psychiatrist at the discretion of the treating endocrinologist.*

Patients randomized to SC will be treated as above but they will not use a CGS during the 9-month Randomized Phase. Given the enrollment criteria for this study, a baseline mean HbA_{1c} for this group can be expected to be about 8.8% and we anticipate a 0.2% increase (~0.15 SD) to about 9.0% during the 9-month randomization phase of the study.

All study participants will receive the above SC regimen. CGS and CGS+BT regimens will differ as below.

Continuous Glucose Sensor (CGS) With consultation from the diabetes team, patients randomized to CGS will select a CGS device for use during the study from among those that can be made available for use in this study. Appropriate training and counseling will be provided by the diabetes nurse to include:

- Parents and youths will be carefully trained in the safe and proper use of the selected CGS device and associated analytic software. *Substantial emphasis will be placed on making treatment decisions suggested by CGS results only after a confirmatory SMBG check is done. CGS use will be portrayed as a supplement to SMBG, not a replacement.* ¹⁴⁹ Training will cover real-time and retrospective analysis of CGS data and appropriate responses to alarms, using a book by H. [name]. ¹⁵⁰ and the JDRF website "Continuous Glucose Monitoring Classroom" that will soon be available for public access.
- Weekly phone contact initiated by the diabetes nurse during the first month of CGS use.
- 24-hour telephone access to an on-call pediatric endocrinologist.
- Week-day telephone access to the diabetes nurse to report device-related problems.

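### Section 5.6 divides cost by each group's own HbA1c change instead of reporting incremental cost per 0.5% HbA1c difference from Standard Care

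*Combined protocol and SAP*

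**What the plan says.** Section 5.6 gives two descriptive measures: a "direct comparison of the estimated costs of SC, CGS and CGS+BT", and "reporting the cost per 0.5% improvement in HbA_{1c} during the study for each group".

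The costs it describes are totals per condition. For staff time, "we will extrapolate the per-patient personnel costs of each of three conditions for the entire 9-month Randomized Phase". For utilization, "The costs for hospitalizations, ER visits and clinic visits will be obtained from the involved medical facilities". For equipment, "The retail costs of CGS devices and supplies will be included". Section 5.8 adds: "All study participants will receive the above SC regimen". So the cost of SC sits inside the total of every arm.

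For the SC arm, Section 5.8 says "we anticipate a 0.2% increase (~0.15 SD) to about 9.0" percent over the 9-month Randomized Phase. It projects about 8.4% for CGS and about 7.4% for CGS+BT.

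The plan does contain incremental elements. Section 5.6 says the time records permit per-patient incremental costs relative to SC. Section 1 commits to reporting incremental costs and, if the groups differ in emergency visits or hospitalizations, "we will calculate the incremental cost for each such event prevented by the CGS and CGS+BT regimens". No section divides incremental cost by the HbA1c difference between groups.

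**The concern.** Section 3.4 sets the question as the costs and benefits of CGS use, with and without the behavioral intervention, relative to standard care. A ratio formed inside one arm does not answer it. The numerator includes care the patient would have received anyway. The denominator ignores what happened to patients who did not get CGS. That comparison is what randomization provides.

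The rule also breaks down for SC. An arm projected to worsen has no improvement to divide by, and the formula returns a negative number that falls further as SC becomes more expensive. If the figures were published as specified, one would have no meaning, and the other two would not be the price of the HbA1c gain attributable to CGS or CGS+BT.

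**Working it through.** **Inputs.** Baseline 8.8%, SD 1.2%, end-of-study SD about 1.5% (Section 5.13). Projected values: SC 9.0%, CGS 8.4%, CGS+BT 7.4% (Section 5.8). No costs are given, so write C_SC, C_CGS and C_BT for the per-patient totals.

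**Check of the plan's projections.** 8.8 + 0.2 = 9.0. 0.2/1.2 = 0.17 SD and 0.2/1.5 = 0.13 SD, which bracket the stated 0.15 SD. 8.8 - 0.3 × 1.2 = 8.44, or about 8.4. The projections reproduce.

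**Planned measure:** cost ÷ [(baseline - month-9 HbA1c)/0.5].

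- SC: C_SC ÷ (-0.2/0.5) = -2.5 × C_SC
- CGS: C_CGS ÷ (0.4/0.5) = 1.25 × C_CGS
- CGS+BT: C_BT ÷ (1.4/0.5) = 0.36 × C_BT

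**Incremental measure:** cost difference ÷ [(between-group HbA1c difference)/0.5].

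- CGS vs SC: (C_CGS - C_SC) ÷ (0.6/0.5) = 0.83 × (C_CGS - C_SC)
- CGS+BT vs SC: (C_BT - C_SC) ÷ (1.6/0.5) = 0.31 × (C_BT - C_SC)
- CGS+BT vs CGS: (C_BT - C_CGS) ÷ (1.0/0.5) = 0.50 × (C_BT - C_CGS). With the 0.8% difference that Section 5.13 uses at 12 months, the multiplier is 0.5/0.8 = 0.625.

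**Size of the gap.** Assume a CGS arm costs r times SC. Planned ÷ incremental (vs SC) is then [r/(r - 1)] × [change vs SC ÷ own change]. The first factor comes from counting SC care in the numerator. The second comes from leaving the SC change out of the denominator: 0.6/0.4 = 1.5 for CGS and 1.6/1.4 = 1.14 for CGS+BT.

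| Assumed r | CGS, planned (× C_SC) | CGS, incremental (× C_SC) | CGS overstatement | CGS+BT overstatement |
|---|---|---|---|---|
| 1.5 | 1.88 | 0.42 | 4.5 | 3.4 |
| 2 | 2.50 | 0.83 | 3.0 | 2.3 |
| 3 | 3.75 | 1.67 | 2.25 | 1.7 |

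**Instability of an SC figure.** A change of +0.05% gives -10 × C_SC, and -0.05% gives +10 × C_SC. With 45 patients, SDs of 1.2 and 1.5 and an assumed within-patient correlation of 0.6, the SD of change is √(1.44 + 2.25 - 2 × 0.6 × 1.2 × 1.5) = 1.24 and its standard error is 1.24/√45 = 0.184. The 95% interval around +0.2% runs from -0.16 to +0.56. Over correlations of 0.5 to 0.8, the chance that the observed SC change has the opposite sign to the projection is about 16% down to 7%.

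**The case against.** The best defense is that the sentence opens by speaking of the cost effectiveness of CGS and CGS+BT, so the groups meant may be those two alone, and that the word cost is never defined. On that reading no SC ratio is computed. This is possible, although all three arms are named just before and the costs described are totals for each condition. It does not rescue the measure. Even with an incremental numerator, a within-arm denominator would still be 0.4% instead of 0.6%, and 1.4% instead of 1.6%.

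It is also fair that the analysis is secondary and descriptive, that Section 3.4 chooses a simple approach on purpose, and that a reader given costs and HbA1c by arm could subtract. These points limit the consequence. They do not make the specified ratio the right one. Section 3.4 sets aside utility-based methods because youths may struggle with the questions, and that reason does not apply to an incremental ratio on HbA1c.

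Several stronger readings are not supported:

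- A reader might infer that a negative figure would present SC as the cheapest arm. Nothing in the plan ranks arms by this ratio. The figure would have no meaning, and it depends on a projection: in the cited trial described in Section 3.7, the SMBG arm fell by 0.3% at 3 months.
- A reader might infer that only the CGS arms carry the whole cost of care. On the natural reading every arm does, SC included.
- A reader might infer that incremental costing is absent. Sections 1 and 5.6 provide for it; only the link to HbA1c is missing.
- A reader might want one fixed factor for the distortion. Without costs in the documents, only a range under a stated assumption is possible, and the comparator must be the same on both sides.

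**Conclusion.** The point holds. The planned ratio does not measure cost effectiveness relative to SC, and on the plan's own projections it gives SC an uninterpretable -2.5 × C_SC if SC is included. If each CGS arm costs 1.5 to 3 times SC, it overstates the incremental ratio versus SC about 2.3- to 4.5-fold for CGS and 1.7- to 3.4-fold for CGS+BT.

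These sizes rest on the assumed cost multiple and on the projected HbA1c values. The denominator part (1.5 and 1.14) depends on SC worsening by 0.2%. If SC improved instead, that part would reverse, because the CGS arms would be credited with improvement that occurs without CGS. The ratio fails to use the randomized comparison in either case. No hypothesis, sample size or primary conclusion depends on it.

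**What to change.** In Section 5.6, make SC the reference and replace the per-group ratio with incremental cost per 0.5% between-group HbA1c difference, for CGS vs SC, CGS+BT vs SC and CGS+BT vs CGS. Fix the HbA1c difference at month 9. The present wording names no visit, costs are extrapolated over 9 months, and SC patients may use CGS from month 9 to month 12.

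Show HbA1c uncertainty through the confidence interval of the between-group difference, and give a sensitivity range for the extrapolated personnel cost. A simple bootstrap over patients is not suitable. Staff time is recorded in only four 2-week windows during project months 18 to 36 (Section 5.6), while recruitment runs from about month 12 to month 36 (Section 5.15). Patients' 9-month phases therefore overlap the windows unequally, late enrollees hardly at all, and the cost is extrapolated per condition.

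The point estimates need no new data. The cost is a short change to the text and a little more analysis work.

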5.7. Measurement schedule. In the measurement schedule below, "P" indicates collection of the measure from parent, "A" = from adolescents and "B" = from both parents and youths. All measures will be translated into Spanish and back-translated into English by native Spanish speakers. Participants may choose whether to complete the English or Spanish versions. Internal consistency and test-retest reliability will be calculated for each measure based upon data collected in the proposed study.

MEASUREMENT SCHEDULE

Measure	Study Visits (Months)				
	0	3	6	9	12
General Information Form (P)	•				
Glucose Meter memory downloads (A)	•	•	•	•	•
CGS Device downloads (A)	•	•	•	•	•
Measures of glycemic variability (A)	•	•	•	•	•
Hypoglycemia Diary (B)	•	•	•	•	•
HbA _{1c} (A)	•	•	•	•	•
7-Day Blinded CGS use (SC only)	•	•	•	•	•
Diabetes Self Management Profile (B)	•	•	•		•
Glucose Monitoring System Rating Scale (B)	•	•	•	•	•
BG Monitoring Communication Questionnaire	•	•	•	•	•
Hypoglycemia Fear Survey (B)	•	•	•	•	•
Diabetes Family Responsibility Questionnaire (B)	•	•	•	•	•
Wiebe Parental Involvement Interview (A)	•	•	•	•	•
Diabetes Responsibility & Conflict Scale (B)	•	•	•	•	•
PedsQL Diabetes Module (B)	•	•	•	•	•
Readiness to Change Questionnaire (B) (CGS+BT only)	•	•	•	•	•
Diabetes Problem Solving Interview (B)	•				

The only copyrighted instrument being administered is the PedsQL quality of life questionnaire, but Nemours owns a site license that permits free use and distribution for research purposes at all Nemours entities. Consequently, it will be possible to enable administration of the various measures via a secure internet connection using the Opinio software platform. This functionality will enable participants to complete questionnaires from anywhere that provides internet access at any time within the 2 week period immediately preceding each quarterly diabetes clinic visit. If participants are unable to accomplish this, the questionnaires will be available for hard-copy administration at clinic visits and they will be encouraged to do so during waiting times before and during their visits. This flexibility should enable participants to control the amount of time dedicated to study participation on clinic visit days.

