Continuous Glucose Sensor Plus Behavior Therapy (CGS+BT) Patients randomized to CGS+BT will receive the same education and care as the CGS group. Also, a mental health professional (MHP; e.g. a licensed counselor, post-doctoral fellow, licensed clinical social worker, or psychologist) will deliver a behavioral intervention within a motivational interviewing context that is designed to identify each family's unique behavioral, cognitive or affective barriers and resources pertaining to optimal CGS use, negotiate with the youth and parent a plan addressing the identified targets, and assist the family in implementing, evaluating and possibly refining the selected intervention over the ensuing months. The MHP's role in this study will be very similar to that of the Health Advisor interventionists in the FMOD trial and we will make extensive use of a manual, intervention handouts, telephone contact protocols, intervention plan outlines and other such materials that were developed in that study. *A preliminary draft of the intervention manual appears in the Appendix, to be further refined prior to initiation of the study. Each MHP will receive extensive training in Motivational Interviewing coordinated by our expert consultant, [name].* The MHP will guide the family in preparing an action plan that will include responsibilities of each family member in implementing it, methods of measuring the plan's effectiveness, and a timeframe for evaluation and refinement of the plan. At a minimum, the MHP will telephone the teen and parent 2 weeks before and 2 weeks after diabetes clinic visits to review the family's success with their plan, and trouble-shoot with them any problems they report in implementation of the plan. Like the diabetes educators, the MHP's will be permitted to make appointments with CGS+BT families for more phone contacts and supplemental face-to-face clinic visits as needed to provide the assistance they need to benefit from CGS. MHP's will see each CGS+BT family at every diabetes clinic visit, including with the Diabetes Nurse or Dietitian as needed. MHP's may target for intervention any problem that a family may report that may be impeding the adolescent from using the CGS optimally. *MHP's will document the date, time, duration and content of all telephone and face-to-face encounters with CGS+BT families.* MHP's will be trained to identify certain negative behaviors related to CGS use that could be intervention targets and to recognize instances in which families could benefit from targeting the promotion of positive behaviors rather than on remediation. Below are some CGS-specific target behaviors that MHP's may select with CGS+BT families. Additional target behaviors are likely to be identified during the study.

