Intervention visits will be scheduled to coincide with other study visits. The MHP will see each CGS+BT family at the Baseline visit, the 2-week and 1-month follow-up nursing visits and each quarterly clinic visit during the 9-month Randomized Phase of the study, for a total of 5 scheduled clinical encounters. Telephone follow-ups will be scheduled at 2-weeks before and 2-weeks after each clinic visit, with more frequent contacts or e-mail communication if deemed necessary by the MHP. MHP's will be allowed to see CGS+BT families for separate face-to-face appointments if needed. The Baseline, 2-week and 1-month visits will be dedicated to delivery of a common psychoeducational curriculum to each CGS+BT family and to initial assessment of each family's current adaptation to T1DM and its management. The content of this curriculum will include basic principles of behavior change, positive reinforcement, problem solving skills, healthy communication, and conflict resolution. Examples of specific behavior change goals related to optimal CGS use will be employed to illustrate each of these principles in that context. The conclusion of the 1-month visit will be dedicated to assisting each family in identifying one or more targeted behaviors related to CGS use, ideally focusing on both positive and negative behavior change goals. CGS+BT visits beginning with the 3-month visit will be dedicated to evaluating and refining the behavior change plan(s) developed at prior visits.

All face-to-face contacts between MHP's and CGS+BT families will be audio-recorded and sent to [name] for evaluation and coding for treatment integrity, using previously developed coding systems used in prior trials. This will include recording of the target behaviors and the type of behavior therapy methods used. Deviations from the intervention manual will result in re-training of the MHP involved as well as possible revision of the intervention manual to clarify sources of ambiguity.

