Statistical analysis will begin with treatment of missing data, preliminary descriptive analysis and visual inspection of distributions.¹⁵⁵⁻¹⁵⁶ Appropriate transformations of variables will be used to restore normality if needed. Baseline values of the primary outcome and predictor variables will be compared to determine if there are significant pretreatment differences between the groups that require adjustments. Visual examination of scatter plots, histograms and other graphical summaries will be used to identify possible associations or treatment effects of interest. Where multiple statistical comparisons are planned, we will make appropriate multiplicity adjustments.¹⁵⁵⁻¹⁵⁸ Internal consistency will be calculated for each psychometric measure based on

data from this study and only those with $\alpha \geq .70$ will enter data analyses. Upon completion of these preparatory activities, we will apply Individual Growth Modeling¹⁶⁰⁻¹⁶¹ to test the hypotheses listed below (see Section 5.12 for details).

5.10. Hypotheses. The following hypotheses, corresponding to the three specific aims, will be tested:

Hypothesis 1: Adolescents in CGS+BT will show more improvement in glycemic control (HbA_{1C}, Kovatchev's measures of glycemic variability derived from SMBG and CGS data, and proportion of CGS values in the normal range) compared with those in SC and CGS over the 9-month Randomized Phase.

Hypothesis 2: Adolescents in CGS+BT will realize more improvement in diabetes-related behavioral outcomes (Diabetes Self-Management Profile; PedsQL Diabetes Module; Diabetes Responsibility and Conflict Scale; Hypoglycemia Fear Survey; Blood Glucose Monitoring Communication Questionnaire: Blood Glucose Monitoring System Rating Questionnaire) compared with those in SC and CGS and in scores on the CGM Satisfaction Scale (CGS vs CGS+BT only) over the 9-month randomization phase of the study.

Hypothesis 3a: Improvements in HbA_{1C} during the 9-month Randomized Phase will be moderated by adolescents' and parents' baseline status on the following measures: Socioeconomic status; Family composition; Adolescent age; Diabetes Problem Solving Interview, Parent-Adolescent Relationship Questionnaire; Diabetes Family Responsibility Questionnaire; Wiebe Parental Supportive Involvement Interview; and Diabetes Responsibility and Conflict Scale).

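### In CGS+BT only, self-report questionnaires may be answered after the pre-visit therapist call or the visit-day session, and nothing fixes the order

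*Combined protocol and SAP*

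**What the plan says.** **Collection.** Section 5.7 allows online completion "at any time within the 2 week period immediately preceding each quarterly diabetes clinic visit". Families who cannot manage this get paper forms at the clinic, where "they will be encouraged to do so during waiting times before and during their visits". The rule is the same in all arms.

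**Therapist contact, CGS+BT only.** Section 5.8 states that, as a minimum, "the MHP will telephone the teen and parent 2 weeks before and 2 weeks after diabetes clinic visits". It repeats this under the intervention schedule: "Telephone follow-ups will be scheduled at 2-weeks before and 2-weeks after each clinic visit". The purpose of the call is to "review the family's success with their plan, and trouble-shoot with them any problems they report in implementation of the plan". Section 5.8 also says "MHP's will see each CGS+BT family at every diabetes clinic visit" and "Intervention visits will be scheduled to coincide with other study visits".

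**Hypothesis.** Section 5.10 states that "Adolescents in CGS+BT will realize more improvement in diabetes-related behavioral outcomes" than those in SC and CGS over the 9-month Randomized Phase.

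**Safeguards.** Section 5.8 keeps MHPs out of recruitment and data collection in order to limit reactivity and bias. Section 1 adds a part-time research assistant at each site so that questionnaires and interviews are kept apart from clinical care and the behavioral intervention. Neither text says whether a form comes before or after an MHP contact, and no text says that completion times are recorded.

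**The concern.** The scales are unblinded self-report, and several ask about matters that the intervention may target, such as arguments over glucose values and family communication about them. Answers given shortly after discussing those matters with a therapist may reflect a momentary response, or a wish to please, as well as durable change. Only CGS+BT families can be in that position. Baseline forms precede randomization and so carry no therapist contact in any arm. A short-term shift at follow-up would therefore enter the change from baseline, which is what Hypothesis 2 tests.

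At stake is the interpretation of the behavioral outcomes and of the questionnaire mediators in Hypothesis 3b.

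**Working it through.** **1. Calendar.** Count days back from a quarterly visit (day 0).
- Online window (5.7): day −14 to day 0. Paper fallback: day 0, before or during the visit.
- MHP call (5.8, CGS+BT only): nominally day −14. MHP meeting: day 0.
- An online answer given after the call therefore follows MHP contact by 0 to 14 days. A paper answer on day 0 may follow a session directly.
- Between the routine visits at months 3, 6 and 9, a quarter is about 13 weeks. The stretch from the call after one visit to the call before the next is 13 − 2 − 2 = 9 weeks. No questionnaire is collected in it unless a form happens to be completed before the call.

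**2. Which outcomes.** Section 5.12 analyses six scales under Hypothesis 2.
- Five are questionnaires: PedsQL Diabetes Module, Diabetes Responsibility and Conflict Scale, Hypoglycemia Fear Survey, Blood Glucose Monitoring Communication Questionnaire, and Glucose Monitoring System Rating Questionnaire.
- The sixth, the Diabetes Self Management Profile, is a telephone interview by coordinating-center staff, with no date given relative to the visit (5.5).
- Section 5.10 also names the CGM Satisfaction Scale, but it is not in the measurement schedule, so I do not count it.
- Of the five Hypothesis 3b mediators, two are questionnaires (the Conflict Scale and the Communication Questionnaire). The other three are interviews, and the Diabetes Problem Solving Interview is scheduled at baseline only.

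**3. How a shift would enter a slope.** The plan gives no figure to reproduce. Assume a constant reporting shift s in CGS+BT at months 3, 6 and 9, none at baseline, complete data and an ordinary linear fit.
- Months 0, 3, 6, 9: deviations from the mean are −4.5, −1.5, 1.5, 4.5, with sum of squares 20.25 + 2.25 + 2.25 + 20.25 = 45. Slope bias = s(−1.5 + 1.5 + 4.5)/45 = 0.1s per month, or 9 × 0.1s = 0.9s over the phase.
- Months 0, 3, 6, 9, 12, with no shift at 12: deviations are −6, −3, 0, 3, 6, with sum of squares 90. Slope bias = s(−3 + 0 + 3)/90 = 0.

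Both fits are open. Hypothesis 2 is worded for 9 months, while section 5.12 describes five time points.

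**4. Illustration only.** Take a single-visit comparison of two means with 45 per arm (the month-9 figure in 5.13), two-sided 5% (assumed, since no alpha is stated) and no lasting effect. With δ = d × √(45/2), the rejection rate is Φ(δ − 1.96) + Φ(−δ − 1.96).

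| Assumed shift d (SD) | δ | Rejection rate |
|---|---|---|
| 0.1 | 0.47 | 7.6% |
| 0.2 | 0.95 | 15.8% |
| 0.3 | 1.42 | 29.6% |

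The shifts are assumptions, and this is not the planned growth model.

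**The case against.** **Contact is part of the treatment.** The MHP's calls and sessions are what CGS+BT adds, so some response to them is the effect under study. This stands, but the plan is interested in change that lasts, and its forms cluster around the contacts.

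**Coaching is inferred.** A reader might infer that Hypothesis 2 compares freshly coached answers with uncoached ones. The documents do not go that far. Online completion before the visit is the default. The call is about the family's own plan, which may concern sensor wear or calibration rather than anything a scale asks. The two-week timing is nominal, so some answers may precede the call. All arms also receive monthly nurse calls (5.8), so the other arms lack MHP contact, not professional contact. The text permits the overlap; it does not show how often it would happen.

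**Month 12 is a check.** Questionnaires are repeated at month 12, and section 5.11 plans a maintenance analysis. Scheduled MHP encounters belong to the 9-month phase. If a call follows the month-9 visit by two weeks, the month-12 window lies 13 − 2 − 2 = 9 to 13 − 2 = 11 weeks after it. This is a real but partial check. A decline by month 12 could be a fading reporting effect or a waning benefit, and section 5.1 would read deterioration of gains as further evidence that the intervention works.

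**Staff are already separated.** True, and worth keeping, but separation of staff does not determine when a form is completed.

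**Conclusion.** The point holds for the self-report questionnaires at months 3, 6 and 9. The plan permits completion after MHP contact in one arm only and does not control or record the order. On five of the six scales analysed under Hypothesis 2 and two of the five Hypothesis 3b mediators, a short-term response cannot be separated from lasting change.

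The size is unknown. Depending on whether month 12 enters a linear fit, a constant shift s would contribute 0.9s over nine months or nothing. The zero assumes that month 12 carries no shift, which is itself inferred from the schedule. It would be wrong to read the rejection rates above as this trial's error rate, to extend the point to the interview measures, or to see a threat to HbA1c, a laboratory assay that does not depend on when forms are filled in. This is a cheap improvement to data collection, not a flaw in the design.

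**What to change.** In section 5.7, for all three arms:
- Hand out visit-day paper forms at check-in, to be completed before any MHP session.
- Open the online window a few days before the nominal pre-visit call date and ask families to finish by that date where possible.
- Store the date and time at which each form is completed.

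In section 5.12, use timing relative to MHP contact only descriptively or in a labelled sensitivity analysis. Do not test Hypothesis 2 in the subset of forms completed before contact: families choose when to answer after randomization, and SC and CGS have no matching contact, so the randomized comparison would be lost.

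The therapy schedule is unchanged. The cost is slightly earlier or wider timing of forms, and a handout-order task for the research assistant already planned at each site. Some answers will still follow the call, but the stored times will show how many.
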